8.4 Secondary Efficacy Analyses

8.4.1 Key Secondary Efficacy Analyses

8.4.1.1 Change in Total Symptom Score (TSS) at Week 24 from Baseline

The total symptom score will be measured by Myelofibrosis Symptom Assessment Form (MFSAF) v4.0.³ The daily TSS scores will be calculated by summing up scores from all 7 questions from the questionnaire. All 7 questions need to be answered to calculate a daily score. [REDACTED]

TSS score at Week 24 is defined as [REDACTED]

TSS scores will be analyzed using a linear mixed effects model with treatment arm, visit, treatment by visit interaction, DIPSS+ risk group (intermediate versus high risk), platelet count ($\leq 200 \times 10^9/L$ versus $> 200 \times 10^9/L$) and baseline score as fixed effects, as described in Section 8.1. An unstructured variance covariance matrix will be used. The compound symmetry variance covariance matrix will be used if the model does not converge with the unstructured matrix. Weekly scores up to Week 24 will be included in the mixed model. Parameter estimation is based on the method of restrictive maximum

likelihood. Within the framework of the mixed model, change in TSS score from baseline at Week 24 will be compared between the treatment and control arm.

The tipping point analysis described in Section 8.2 will be performed as a sensitivity analysis to assess departure from the MAR assumption. For subjects who do not have Week 24 TSS score, reasons for missing Week 24 TSS score will be summarized for each treatment arm and individual scores prior to Week 24 will be plotted to explore the validity of the missing at random assumption.

The following supplementary analyses will be performed:

- Change in TSS score at Week 24 from baseline by excluding the fatigue item
- TSS_{50W24} rate
- TSS₅₀ rate at any time
- Time to first TSS₅₀
- Duration of TSS₅₀
- TSS response rate at any time based on meaningful change threshold (MCT)
- TSS response rate at Week 24 based on meaningful change threshold (MCT)
- Time to first TSS response based on MCT
- Duration of TSS response based on MCT.

TSS_{50W24} rate is defined as the proportion of subjects who achieve at least 50% reduction in total symptom score at Week 24 from baseline. TSS scores obtained after confirmed disease progression or start of post-study treatment will not be included in the analysis. Subjects who do not have TSS score at Week 24 will be treated as non-responders. Subjects who do not receive any study drug will be treated as non-responders. TSS_{50W24} rate will be analyzed using the statistical method described for binary variables in Section 8.1.

TSS₅₀ rate any time is defined as the proportion of subjects who achieve at least 50% reduction in total symptom score from baseline at any time during the study. TSS scores obtained after confirmed disease progression or start of post-study treatment will not be

included in the analysis of TSS₅₀ rate. Subjects who do not have any TSS score after randomization will be treated as non-responders. Subjects who do not receive any study drug will be treated as non-responders. TSS₅₀ rate will be analyzed using the statistical method described for binary variables in Section 8.1.

Time to first TSS₅₀ is defined as the time from randomization to the first date of achieving TSS₅₀. Time to first TSS₅₀ will be summarized descriptively for each treatment arm.

Duration of TSS₅₀ is defined as the time from the first date of achieving TSS₅₀ to the first date of loss of TSS₅₀. Loss of TSS₅₀ is defined as not maintaining TSS₅₀ and at least 50% increase in TSS from nadir (the lowest score in the previous weeks). Subjects who do not lose TSS₅₀ response will be censored at the last TSS assessment. Subjects with ≥ 2 consecutive missing TSS scores prior to losing TSS₅₀ response will be censored at the last non-missing TSS assessment prior to losing TSS₅₀ response. The distribution of duration of TSS₅₀ will be estimated for each treatment arm using Kaplan-Meier methodology. Median duration of TSS₅₀ and the corresponding 95% confidence interval will be provided for each treatment arm. Only subjects who achieve TSS₅₀ at any time will be included in the analysis of duration of TSS₅₀.

TSS response rate at any time during the study is defined as proportion of subjects who achieved change in TSS score from baseline \leq MCT at any time during the study. The MCT, derived using anchor-based analyses, has been determined to be at least 10 points for improvement in TSS from baseline. The validation of MCT of -10 is described in the Psychometric Analysis Report. TSS scores obtained after confirmed disease progression or start of post-study treatment will not be included in the analysis of TSS response rate. Subjects who do not have any TSS score after randomization will be treated as non-responders. Subjects who do not receive any study drug will be treated as non-responders. TSS response rate will be analyzed using the statistical method described for binary variables in Section 8.1. Similar analyses will be performed for TSS response rate at Week 24. The maximum reduction in TSS from baseline at any time will be summarized.

Time to TSS response is defined as the time from randomization to the first date of achieving TSS response based on MCT of at least 10 points. Time to first TSS response will be summarized descriptively for each treatment arm.

Duration of TSS response is defined as the time from the first date of achieving TSS response to the first date of loss of TSS response. Loss of TSS response is defined as diminishment of TSS below MCT improvement of 10 points. Subjects who do not lose TSS response will be censored at the last TSS assessment. Subjects with ≥ 2 consecutive missing TSS scores prior to losing TSS response will be censored at the last non-missing TSS assessment prior to losing TSS response. The distribution of duration of TSS response will be estimated for each treatment arm using Kaplan-Meier methodology. Median duration of TSS response and the corresponding 95% confidence interval will be provided for each treatment arm. Only subjects who achieve TSS response at any time will be included in the analysis of duration of TSS response. Sensitivity analysis of duration of TSS response may be performed by accounting for disease progression or death.

In addition, descriptive summaries of weekly TSS scores and individual symptom scores, change from baseline and percent change from baseline will be provided for each treatment arm. Change and percent change in TSS scores and individual symptom scores from baseline at Week 24 may also be presented graphically for each treatment arm.

TSS analyses will be performed on the ITT population. Sensitivity analyses will be performed using the TSS Sensitivity Analysis Population described in Section 4.0.

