8.0 Efficacy Analyses

8.1 General Considerations

Unless otherwise specified, all randomized subjects in the ITT population will be included in the efficacy analyses. All statistical tests will be 2-sided at an alpha level of 0.05.

The primary analysis will be performed after all ongoing subjects have completed 24 weeks of follow-up and the database has been locked. Unless otherwise specified, data after the cutoff date will be excluded from statistical analyses.

Unless otherwise specified, all subjects will be analyzed according to the baseline platelet count and DIPSS+ score collected in Electronic Data Capture (EDC) system. For subjects with missing karyotype information, the DIPSS+ score will be calculated by assuming these subjects do not have unfavorable karyotype. The DIPSS+ score will be categorized by intermediate (including both intermediate-1 and intermediate-2) and high risk.

Unless otherwise specified, binary variables (e.g., response rates) will be analyzed using Cochran-Mantel-Haenszel (CMH) test, stratified by DIPSS+ risk group (intermediate versus high risk) and platelet count ($\leq 200 \times 10^9/L$ versus $> 200 \times 10^9/L$). The 95% confidence interval for the response rate will be provided for each treatment arm using the exact binomial distribution. The strata-adjusted difference in the response rates between the treatment arms and the 95% confidence interval for the difference will also be provided.

Unless otherwise specified, continuous data from patient-reported outcome will be analyzed using linear mixed effects model with treatment arm, visit, treatment by visit interaction, DIPSS+ risk group (intermediate versus high risk), platelet count ($\leq 200 \times 10^9/L$ versus $> 200 \times 10^9/L$) and baseline score as fixed effects. An unstructured variance covariance matrix will be used. The compound symmetry variance covariance matrix will be used if the model does not converge with the unstructured matrix. Change in score from baseline will be compared between the treatment arms for the specified post-baseline visit. The least-squares mean change from baseline and the corresponding 95% confidence interval will be provided for each treatment arm. In addition, the least-squares mean of the difference between the treatment arms and the corresponding 95% confidence interval will be provided.

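### The mixed model for weekly TSS uses one baseline slope for all visits; if the link to baseline fades by Week 24, the Week 24 contrast loses some precision that a baseline-by-visit term would recover

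*SAP*

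**What the plan says.** SAP 8.1 sets a general mixed model for continuous patient-reported outcomes, and SAP 8.4.1.1 repeats it for TSS: "TSS scores will be analyzed using a linear mixed effects model with treatment arm, visit, treatment by visit interaction, DIPSS+ risk group", platelet group "and baseline score as fixed effects, as described in Section 8.1". Three further statements matter here.

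- Visits: "Weekly scores up to Week 24 will be included in the mixed model".
- Covariance: "An unstructured variance covariance matrix will be used", with a fallback: "The compound symmetry variance covariance matrix will be used if the model does not converge with the unstructured matrix".
- Test: "change in TSS score from baseline at Week 24 will be compared between the treatment and control arm", two-sided at 0.05.

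Baseline score is a main effect only, and neither document adds a baseline-by-visit term elsewhere. The redactions in SAP 8.4.1.1 fall in the score definitions; the sentence that lists the model terms is complete.

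SAP Table 1 ranks this endpoint second, directly after SVR35W24. SAP 8.4.1.3 and 8.4.1.5 apply the same general model to PROMIS Fatigue and physical functioning, which are ranked eighth and ninth.

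**The concern.** With only a main effect, the model assumes that one point of baseline TSS predicts the same number of points at Week 1 and at Week 24. Week 1 directly follows baseline. Week 24 follows about six months of active treatment in both arms, in subjects who had to be symptomatic to enter. If improvement is uneven, the Week 24 score will depend less on baseline than the Week 1 score does.

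The common slope is then a compromise. Under an unstructured covariance that reflects fading correlation, the early weeks carry most of the weight, because residuals given baseline are smallest there. The Week 24 contrast is adjusted with a slope that is too steep for Week 24, and the mismatch adds to the Week 24 residual variance.

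What is at stake is power. Testing follows a fixed sequence, so failure on TSS blocks ranks 3 to 9, including overall survival. The documents state no power for TSS, so no margin can be taken for granted.

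**Working it through.** **Inputs from the documents.** About 230 subjects randomised 1:1, so 115 per arm (Protocol 7.7); weekly visits up to Week 24, taken as 24 post-baseline visits; unstructured covariance; two-sided 0.05. The documents give no TSS standard deviation, visit correlation, expected difference or power. There is therefore no planned figure to reproduce, and every correlation below is an assumption.

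**Formulas (large sample, complete data).** Let B be the vector of visit-specific baseline slopes, S the residual covariance between visits given baseline, and **1** a vector of ones.

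- Common slope: b = (**1**′S⁻¹B) / (**1**′S⁻¹**1**).
- Week 24 SE ratio, common slope against baseline by visit: √[1 + (B₂₄ − b)² × Var(baseline) / S₂₄], where S₂₄ is the Week 24 residual variance.
- Power, if the better model had 90%: Φ[(1.960 + 1.282)/ratio − 1.960]. The 90% is a reference level only.

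**Correlation structures.** All variances are set to 1. The correlation between weeks s and t is a stable part plus a decaying part × ρ^|s−t|; the remainder is week-specific noise.

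**One case in full.** Stable 0.3, decaying 0.6, ρ = 0.95, noise 0.1.

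- Slopes: Week 1 = 0.3 + 0.6 × 0.95 = 0.87; Week 24 = 0.3 + 0.6 × 0.95²⁴ = 0.475.
- Common slope: b = 0.792, with 78% of the weight on Weeks 1 to 4.
- S₂₄ = 1 − 0.475² = 0.774.
- Ratio = √[1 + (0.475 − 0.792)²/0.774] = √1.130 = 1.063.
- Power = Φ(3.242/1.063 − 1.960) = 86.2%.

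**Range of cases.** The last column uses an equal-weight average slope, which approximates the compound symmetry fallback.

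| Assumed pattern | Slope Wk 1 | Slope Wk 24 | Common slope | Weight Wk 1–4 | SE ratio | 90% becomes | SE ratio, averaged slope |
|---|---|---|---|---|---|---|---|
| Constant correlation 0.5 | 0.50 | 0.50 | 0.50 | 17% | 1.000 | 90.0% | 1.000 |
| 0.4 / 0.3, ρ 0.80 | 0.64 | 0.40 | 0.50 | 44% | 1.006 | 89.7% | 1.001 |
| 0.4 / 0.4, ρ 0.90 | 0.76 | 0.43 | 0.64 | 61% | 1.026 | 88.5% | 1.007 |
| 0.3 / 0.6, ρ 0.95 | 0.87 | 0.48 | 0.79 | 78% | 1.063 | 86.2% | 1.017 |
| 0.2 / 0.7, ρ 0.95 | 0.87 | 0.40 | 0.77 | 78% | 1.078 | 85.2% | 1.021 |
| 0.3 / 0.6, ρ 0.95, SD falling by a quarter | 0.82 | 0.36 | 0.66 | 65% | 1.102 | 83.7% | 1.025 |
| Pure AR(1), Week 24 correlation 0.3 | 0.95 | 0.30 | 0.90 | 91% | 1.182 | 78.3% | 1.038 |

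Other pure AR(1) cases, with Week 24 correlation 0.2 to 0.5, gave ratios of 1.13 to 1.20. With Week 24 correlation 0.2 or 0.3, the common slope did worse than no baseline adjustment at all (1.20 against 1.02, and 1.18 against 1.05).

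**Simulation check.** There were 400 trials per scenario with n = 230, an unstructured fit, and 8 visits instead of 24 for speed. For the 0.3 / 0.6, ρ 0.95 pattern, the empirical SE ratio was 1.073 with complete data and 1.063 with about 19% missing-at-random dropout. Bias was about zero. Across scenarios, rejection under the null with the common-slope model was 0.040 to 0.065. The simulation standard error is √(0.05 × 0.95/400) = 0.011, so these values are compatible with 0.05.

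**The case against.** The strongest reply is that the loss is hypothetical. A reader might infer from the model statement that the Week 24 standard error is certainly inflated by a material amount. The documents do not support that. With a constant baseline association the ratio is exactly 1. A separate set of ten assumed structures, with Week 24 correlations of 0.30 to 0.62, gave inflation of only 0.2% to 4.1%. A low Week 24 correlation does not by itself produce a large loss. This stands, and the range must include zero.

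A reader might also infer that the TSS test is biased or invalid. It is not: randomisation protects the contrast, and the simulations showed neither bias nor a raised null rejection rate.

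The fallback also weakens the point. With 24 visits the unstructured matrix has 24 × 25/2 = 300 parameters for about 230 subjects, so compound symmetry may well be what is fitted. The slope is then close to an average over weeks and the loss is about 0% to 4%. This stands too.

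Finally, the tipping point analysis in SAP 8.2 fits an ANCOVA to imputed Week 24 scores, which has its own Week 24 slope. That is correct, but it is a sensitivity analysis and does not replace the ranked test. It also means that the main and sensitivity analyses adjust for baseline differently.

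**Conclusion.** The point holds as a conditional matter of precision. The SAP fits one baseline slope for all weekly visits. If the association with baseline fades, an unstructured fit sets that slope largely from the early weeks, and the Week 24 contrast is less precise than the data allow.

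The size depends on correlations that the documents do not give:

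- constant association: no loss;
- fading association: mostly about 1% to 8% on the standard error;
- strong decay: above 10%;
- compound symmetry fallback, approximated by an averaged slope: about 0% to 4%.

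For fatigue and physical functioning, which have three scheduled post-baseline assessments up to Week 25 Day 1 (Protocol Appendix D), the gain is about 1% to 4% at most. Those ranks cannot be claimed until all ranks above them succeed, so the practical effect there is small.

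Type I error was checked only under the unstructured fit with 8 visits. No error of validity is shown, and the label is a cheap improvement.

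**What to change.** Before unblinding, add a baseline-score-by-visit interaction to the TSS model in SAP 8.4.1.1, and state that the Week 24 treatment contrast is estimated at the overall mean baseline. The same term can be added to the general model in SAP 8.1, so that it covers PROMIS Fatigue and physical functioning.

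The cost is one term in the model statement. With 24 weekly visits, 24 slopes replace one, which is at most 23 extra mean parameters with about 230 subjects. It uses data already collected and leaves the estimand unchanged. If the slopes turn out to be constant, little is lost. The one drawback is slightly more demand on convergence in a model that already has a large covariance matrix, so the fallback should be stated for the extended model as well.

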APPENDIX D. ACTIVITY SCHEDULE

The following table shows the required activities. The individual activities are described in detail in the **Operations Manual**.

Study Activities Table

Activity	Screening/ Baseline	Week 1	Week 1	Week 2	Week 3	Week 5	Week 7	Week 9	Week 13, 17, 21, 25	Q12 weeks as of Week 37	Treatment Completion Visit	30-Day Safety Visit (± 3 Days)	Post-Treatment Visits (± 3 Weeks)	Survival Follow Up
	Day -28 to Day -1	Day 1	Day 2	Day 1 (± 1 day)	Week 13, 17, 21 Day 1 (± 2 days). Week 25 Day 1 (± 3 days)	From Week 37 Day 1 (± 4 days)								
INTERVIEWS & QUESTIONNAIRES														
Informed consent	✓													
Eligibility criteria	✓													
Medical/surgical/transfusion history	✓	✓												
Alcohol and nicotine use	✓													
Adverse event assessment	✓	✓	✓	✓	✓	✓	✓	✓	✓	✓	✓	✓		
Prior/concomitant therapy/transfusion	✓	✓	✓	✓	✓	✓	✓	✓	✓	✓	✓			
Post-treatment therapy/transfusion/surgery												✓	✓	✓
MFSAF v4.0 (Daily)	✓	✓ (Daily through end of Week 36)												
EORTC QLQ-C30 v3.0		✓				✓			✓ (Week 13, 25)	✓	✓			
PROMIS Fatigue SF 7a	✓	✓				✓			✓ (Week 13, 25)	✓	✓			
EQ-5D-5L		✓				✓			✓ (Week 13, 25)	✓	✓			
PGIC									✓ (Week 13, 25)					

Activity	Screening/ Baseline	Week 1	Week 1	Week 2	Week 3	Week 5	Week 7	Week 9	Week 13, 17, 21, 25	Q12 weeks as of Week 37	Treatment Completion Visit	30-Day Safety Visit (± 3 Days)	Post-Treatment Visits (± 3 Weeks)	Survival Follow Up
	Day -28 to Day -1	Day 1	Day 2	Day 1 (± 1 day)	Week 13, 17, 21 Day 1 (± 2 days). Week 25 Day 1 (± 3 days)	From Week 37 Day 1 (± 4 days)								
PGIS	✓	✓							✓ (Week 13, 25)					
ECOG performance status	✓	✓		✓	✓	✓	✓	✓	✓	✓	✓			
Survival follow-up call (approximately every 2 months for up to 8 years)														✓
LOCAL LABS & EXAMS														
MRI (or CT scan) for spleen assessment	✓								✓ (Week 13, 25)	✓ (Week 37, 49, 73, 97)	✓		✓	
12-lead ECG	✓					✓					✓			
Vital signs: including height (Screening only), weight, BP, pulse, and body temperature	✓	✓		✓	✓	✓	✓	✓	✓	✓	✓	✓		
Physical examination including skin examination, spleen and liver measurement by palpation	✓	✓		✓	✓	✓	✓	✓	✓	✓	✓		✓	
Disease Assessment by IWG									✓ (Week 13, 25)	✓ (Week 37, 49, 73, 97)	✓		✓	
Serum/urine pregnancy test	✓	✓				✓		✓	✓ (monthly from Week 25 where a	✓ (monthly where a regulatory requirement)	✓			

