Unless otherwise specified, time-to-event endpoints will be analyzed using Kaplan-Meier methodology and compared between treatment arms using the log-rank test, stratified by DIPSS+ risk group (intermediate versus high risk) and platelet count ($\leq 200 \times 10^9/L$ versus $> 200 \times 10^9/L$). The hazard ratio between treatment arms and the corresponding 95% confidence interval will be estimated using the Cox proportional hazards model, stratified by DIPSS+ risk group (intermediate versus high risk) and platelet count ($\leq 200 \times 10^9/L$ versus $> 200 \times 10^9/L$).

Unless otherwise specified, if a subject prematurely breaks the blind, data after the blind break will be included in the statistical analysis as appropriate based on the definition and analysis of the efficacy endpoints.

Unless otherwise specified, baseline refers to the last non-missing observation before the first administration of study drug or randomization if no study drug is given.

Unless otherwise specified, a confirmed disease progression is defined as any of the following:

- Two consecutive disease responses of progressive disease or relapse, in which case the date of the confirmed disease progression will be the date of the first progressive disease or relapse

- A progressive disease due to leukemic transformation
- A progressive disease or relapse that is the last disease response of a subject.

At the time this SAP is written, the evidence-based MCT for change from baseline in TSS at Week 24 is determined to be –10.

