8.4.1.9 Duration of SVR₃₅

Duration of SVR₃₅ is defined as the time from the first date of SVR₃₅ to the first assessment where SVR₃₅ is not maintained and the spleen volume is $\geq 25\%$ increase from nadir (the lowest spleen volume in the previous assessments), confirmed relapse or leukemic transformation per IWG criteria, whichever is earlier. Subjects without the

defined events will be censored at the date of the last spleen volume assessment, the last disease assessment, the last bone marrow assessment, or the last hematology lab test, whichever occurs the latest and on or prior to the start of the post-study treatment.

The distribution of duration of SVR₃₅ will be estimated for each treatment arm using Kaplan-Meier methodology. Median duration of SVR₃₅ and the corresponding 95% confidence interval will be provided for each treatment arm. There will be no statistical comparison for duration of SVR₃₅.

Only subjects who achieve SVR₃₅ will be included in the analysis.

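### Duration of MCT-based TSS response ends at a single weekly score below the 10-point cut-off, with no confirmation, so fluctuation near the threshold counts as loss and durations may be understated

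*SAP*

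**What the plan says.** All of the following is in SAP section 8.4.1.1 unless another place is named.

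- **Entry.** A subject responds at the first change from baseline at or beyond the MCT, which "has been determined to be at least 10 points for improvement in TSS from baseline". One score is enough.
- **Duration.** It is "the time from the first date of achieving TSS response to the first date of loss of TSS response".
- **Loss.** "Loss of TSS response is defined as diminishment of TSS below MCT improvement of 10 points". No second score, tolerance band or rise from nadir is mentioned.
- **Scores.** The section refers to "descriptive summaries of weekly TSS scores and individual symptom scores", and Protocol Appendix D collects the questionnaire "Daily through end of Week 36". A subject therefore has at most about 36 weekly scores. How daily scores become a weekly score is redacted.
- **Missing weeks.** A subject is censored only when two or more scores in a row are missing before loss.
- **Reporting.** A Kaplan-Meier median with a 95% confidence interval is given per arm, among responders. The only sensitivity analysis mentioned for this duration is optional and deals with progression or death.

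Other rules in the SAP ask for more than one threshold crossing. Loss of TSS50 (section 8.4.1.1) also needs a rise of at least 50% from nadir. Loss of SVR35 through spleen volume (section 8.4.1.9) also needs a rise of at least 25% from nadir. Confirmed progression (section 8.1) is in general "Two consecutive disease responses of progressive disease or relapse", with exceptions for leukemic transformation and for a last assessment.

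**The concern.** Entry and exit use one cut-off on a score that fluctuates from week to week. A subject at 10.2 points of improvement one week and 9.8 the next has a recorded duration of one week, whatever happens afterwards. After entry, a responder can have up to about 35 further weekly scores, and each is an opportunity for one chance crossing. A single missing week is bridged, but a single week just short of 10 points ends the response for good.

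The bias runs towards shorter durations. It also depends on how far a subject's improvement lies beyond 10 points. An arm with a larger average improvement could therefore show longer durations even if benefit faded in neither arm. The secondary objective on onset, magnitude and duration of disease response names TSS, and a median per arm will be reported, so readers will take it as a statement about durability.

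**Working it through.** **What can be checked.** The plan states no expected duration and no week-to-week variability for TSS, so there is no figure to reproduce. The cut-off (10 points), the weekly scores and the 36-week limit come from the documents. The SDs, correlations, true improvements and onset speeds below are assumptions.

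**Step 1: one stable responder.** Let the true improvement exceed 10 points by *d*, with weekly within-subject SD *s* and independent weeks. The chance that a given week falls short is p = Φ(−d/s). The chance of at least one false loss in 24 weeks is 1 − (1 − p)^24.

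| d | s | p | At least one false loss in 24 weeks |
|---|---|---|---|
| 2 | 1 | 0.0228 | 42% |
| 2 | 3 | 0.2525 | 99.9% |
| 5 | 1 | about 0 | about 0% |
| 5 | 2 | 0.0062 | 14% |
| 5 | 3 | 0.0478 | 69% |
| 8 | 2 | 0.00003 | 0.1% |
| 8 | 3 | 0.0038 | 9% |

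The result therefore depends almost wholly on d/s, and the documents give neither quantity.

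**Step 2: subjects who truly respond, none of whom truly loses response.** The simulation used 36 weekly scores per subject. Plateau improvement was drawn from a normal distribution with mean 14 and SD 8, kept only where it was at least 10 points, and held constant once reached. The noise was first-order autoregressive with correlation 0.3 to 0.6. Share declared lost:

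| Onset | Weekly SD | Single-week rule | Two consecutive weeks |
|---|---|---|---|
| Slow (exponential, 4-week time constant) | 3 | 49–56% | 32–33% |
| Slow | 4 | 61–69% | 42% |
| Fast (linear, plateau at Week 4) | 3 | 40–44% | 25–28% |
| Fast | 4 | 53–58% | 35–37% |

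At fast onset and SD 3, the single-week figure is about 43% at correlation 0.3 and 40% at 0.6.

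**Step 3: the mild end.** With every subject at a fixed true improvement, plateau by Week 4 and correlation 0.5:
- Improvement 15, SD 2: 17% declared lost under the single-week rule against 2% with two weeks; neither median is reached.
- Improvement 20, SD 3: 3% against 0%.
- Improvement 15, SD 3: 70% (median 19 weeks) against 24% (median not reached).

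**Step 4: would a nadir condition do the job?** In the last case of Step 3, adding a 50% rise from nadir moves the median only from 19 to 22 weeks. The nadir is itself a noisy minimum, so the extra condition is easily met once noise is appreciable. It helps when noise is small. In a mixed population with mean improvement 12, SD 8 between subjects and weekly SD 1, the share declared lost falls from 27% to about 0%. Two-week confirmation is the more useful change at the SDs where the problem is large.

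**The case against.** **Time continuously at or above the MCT is a legitimate and transparent quantity, and the SAP's version 3.0 history shows that the duration definitions were revised deliberately.** This stands in part: the rule is clear and can be programmed. But the SAP does not hold strictly to continuity, since it bridges a single missing week, and it gives no reason for treating one marginally low week as final.

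**The size rests on assumed noise.** This stands. A weekly score that averages several days would have a smaller SD, and the redaction prevents a check.

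**Some short durations are not understated benefit.** This also stands. If everyone who crosses the line is counted, then in the slow-onset model at SD 3 to 4 about 21% to 26% of recorded responders have a true improvement below 10 points, and they supply 33% to 35% of the losses. That is why Step 2 is limited to subjects with true improvement of at least 10 points.

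**A reader might infer that durations are heavily understated, with medians of only 2 to 8 weeks.** The documents do not support that. Those medians come from the slow-onset model at SD 3 to 4 with chance entrants included. Onset speed alone matters greatly: for a fixed true improvement of 16 points, SD 3 and correlation 0.3, the single-week median is about 5 weeks with slow onset and about 29 weeks if roughly 95% of the plateau is reached by Week 4.

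**A reader might also infer that the TSS50 loss rule avoids the problem.** Step 4 shows that a nadir condition alone helps little at SD 3.

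**The analysis is minor, and persistence is visible elsewhere.** Weekly TSS summaries and the MCT response rate at Week 24 are also planned. That limits the importance, but neither display repairs the reported median duration.

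**Conclusion.** The point holds as a possible understatement of unknown size. As written, one weekly score with less than 10 points of improvement ends the response, and fluctuation near the threshold is counted as loss. With no true loss in any subject, the assumed scenarios run from negligible (SD 1 to 2 with improvement well beyond 10 points) to large. At SD 3 to 4, about 40% to 69% of subjects with true improvement of at least 10 points are declared lost, against about 25% to 42% with two-week confirmation. These figures rest on the assumed SD, correlation, spread of improvement and onset speed.

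The consequence is confined to a descriptive result. Protocol section 3.3 lists the endpoint as exploratory, SAP section 3.3 lists it among the other endpoints, and section 8.4.1.1 makes it supplementary. It is absent from the testing sequence in SAP section 12.0. The primary endpoint and the ranked secondary endpoints, including change in TSS at Week 24, are untouched.

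**What to change.** In SAP section 8.4.1.1, define loss of TSS response as two consecutive non-missing weekly scores with improvement below 10 points, dated at the first of the two. Keep the single-week rule as a sensitivity analysis. If the sponsor prefers the present rule as the main one, the least that is needed is to pre-specify the confirmed-loss version as the sensitivity analysis. The text should also say how a low score followed by two or more missing weeks is handled under the existing censoring rule.

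The cost is about one SAP sentence and a small program change. It should be settled before unblinding, since a confirmation rule chosen afterwards would look data-driven.

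There are two limitations. A loss first seen in the last scored week cannot be confirmed and is censored. Single-score entry is unchanged, so some chance responders remain, both in this analysis and in the response rate at any time. With all entrants counted, slow onset and SD 3 to 4, two-week confirmation still leaves 47% to 57% declared lost.
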